3.5 Objectives

Primary Objective: To determine the impact of a restrictive fluids strategy (vasopressors first followed by rescue fluids) as compared to a liberal fluid strategy (fluids first followed by rescue vasopressors) on 90-day in-hospital mortality in patients with sepsis-induced hypotension.

Primary Hypothesis: Restrictive (vs liberal) fluid treatment strategy during the first 24 hours of resuscitation for sepsis-induced hypotension will reduce 90-day in-hospital mortality.

3.6 Endpoints

3.6.1 Primary Outcome

The primary outcome is all-cause mortality prior to discharge home before day 90. “Home” is defined as a patient’s place of residence prior to enrollment. Thus, if a patient is discharged to a location that is different from the place of residence prior to enrollment (e.g. rehabilitation facility or hospice) then the patient will be followed until they return to their original location, 90 days, or death, whichever comes first.

3.6.2 Secondary Outcomes

1. 28-Day Organ Support Free Days

Organ support free days is defined as a patient being alive and without assisted breathing, new renal replacement therapy, or vasopressors (beyond 48 hours). Patients will be followed for use of organ support to death, hospital discharge or study day 27, whichever comes first. Any day that a patient is alive and without organ support will represent days alive and free of organ support. Since there will be a bias in the protocols to place patients on vasopressors in the restrictive group, vasopressor use prior to 48 hours will be excluded from this calculation for both groups.

2. 28-day Ventilator Free Days (VFDs)

VFDs depend on both duration of ventilation and mortality through study day 28. In participants who survive 28 days, VFD is defined as 28 minus duration of ventilation. Duration of ventilation is counted from the first study day of assisted breathing through the last day of assisted breathing provided the last day is prior to day 28. Otherwise, it is counted from the first study day of assisted breathing through day 28. For participants discharged with assisted ventilation (e.g., to LTAC facility) prior to day 28, a phone call will be required to assess ventilator and vital status at day 28. Participants discharged prior to day 28 on unassisted breathing will be assumed to remain on unassisted breathing through day 28. Isolated periods of ventilation briefer than 24 hours for surgical procedures and ventilation solely for sleep disordered breathing do not count towards duration of ventilation. In participants who never require assisted breathing, duration of ventilation is zero. Participants who do not survive 28 days will be assigned zero VFD. VFD is undefined in participants with chronic/home mechanical ventilation (except solely for sleep disordered breathing) and they will be excluded from this analysis.

3. 28-day Renal Replacement Therapy Free Days

Renal replacement free days to day 28 are defined as the number of calendar days between randomization and 28 days later that the patient is alive and without new renal replacement therapy. We also follow the “last off” method. Patients who died prior to day 28 and those who receive renal replacement therapy for the entire first 28 days are assigned zero renal replacement free days.

4. 28-day Vasopressor Free Days

Vasopressor free days to day 28 are defined as the number of calendar days between day 2 (eligibility starting 48 hours post randomization) and 26 days later that the patient is alive and without the use of vasopressor therapy. We also followed the “last off” method. Patients who died prior to day 28 and those who receive vasopressor therapy for the entire first 28 days are assigned zero vasopressor free days.

5. 28-day ICU free days

ICU free days to day 28 are defined as the number of days spent alive out of the ICU to day 28.

6. 28-day hospital free days

Hospital free days to day 28 are defined as 28 days minus the number of days from randomization to discharge home. If a patient has not been discharged home prior to study day 28 or dies prior to day 28, hospital free days will be zero. Patients transferred to another hospital or other health care facility will be followed to day 28 to assess this endpoint.

7. Initiation of mechanical ventilation to day 28

Patients who receive invasive mechanical ventilation via endotracheal or tracheostomy tube, except those intubated solely for a procedure and extubated within 24 hours, through to study day 28 meet this endpoint. Non-invasive mechanical ventilation will not be included as an outcome. This is a binary outcome.

8. Initiation of renal replacement to day 28

Patients who receive (new) renal replacement therapy through day 28 will meet this endpoint. Patients with chronic renal replacement therapy initiated prior to the current sepsis illness will not be eligible to meet this endpoint.

9. Change in creatinine-based KDIGO stage between baseline and 72 hours

Renal function will be assessed using the KDIGO staging system (serum creatinine criteria only; not urine output) between baseline and 72 hours to assess for de novo acute kidney injury (AKI) (e.g., meeting criteria for AKI by KDIGO criteria) or worsening AKI (e.g., increasing severity). Due to the potential influence of treatment assignment on urine output, as well as the potential for inaccurate urine output data in patients without indwelling urinary catheters, we will use only the KDIGO creatinine criteria. Patients on chronic renal replacement therapy will not be eligible for this endpoint determination.

10. Change in SOFA score between baseline and 72 hours

We will calculate the SOFA score upon enrollment and at 72 hours using clinically available data. If a value is not available at baseline, it will be assumed to be normal. At the 72 hours assessment, if a value is missing then we will carry forward the closest previously known value. If a patient is intubated or heavily sedated at either 0 or 72 hours, the GCS will be omitted when calculating the change in score. If a patient was on renal replacement therapy prior to presentation, then the renal dysfunction component to the SOFA score will be omitted as well. (See Appendix C)

11. 90-day all-cause mortality

We will contact patients at day 90 to ascertain their survival status. This will be done by telephone contact with the patient or family members as well as a review of medical records and publicly available data sources. We will use the national death index as a final check for patient with whom we are unable to confirm their vital status through other means.

12. Development of ARDS within 7 days

We will determine the presence and severity of ARDS for each day of mechanical ventilation to day 7 using the following approach: for each ventilator day, if an ABG is available between 2:00 AM and 8:00 AM, measure P/F (PaO₂, FiO₂ and PEEP) for all ABGs during this time window daily to day 7. Or, for ventilator days that no ABG available between 2:00 AM and 8:00 AM, determine lowest imputed P/F from measured S/F (SpO₂, FiO₂, and PEEP).

For participants with P/F <300 or imputed P/F <300, FiO₂ ≥40%, and PEEP ≥5 cm H₂O, determine if hypoxemia is valid, acute, and not fully explained by CHF or fluid overload. If yes, local investigators will review the first CXR (or CT) performed on each ventilated day with valid P/F or imputed P/F <300 (to day 7). If no chest imaging studies are present that day, site investigators may review available imaging one day before or after to determine if ARDS imaging criteria met. ARDS imaging criteria are met if the images are consistent with ARDS (bilateral opacities not fully explained by effusions, lobar/lung collapse, or nodules). If equivocal, the reviewing investigator will adjudicate with additional investigators.

13. Change in Circulating soluble IL-6 levels over 72-hours

In order to assess the impact of the resuscitation strategy on the inflammatory response, we will collect blood specimens and measure circulating soluble IL-6 at enrollment, and then at 24, and 72 hours.

14. Supraventricular/ventricular tachycardia (SVT/VT) or new onset atrial fibrillation/flutter (AF) to day 28

The occurrence of one or more episodes (sustained for more than 1 minute for SVT and AF, > 15 seconds for VT) during through day 28 will be recorded.

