1.2 Definitions

Adverse Event: Any untoward medical occurrence associated with the use of a drug or a study procedure, whether or not considered drug related.

Adverse reaction: An adverse reaction means any adverse event caused by a study intervention. An adverse reaction is a subset of all suspected adverse reactions where there is a reason to conclude that the study intervention caused the event.

Assisted Ventilation (or Assisted Breathing): any level of ventilatory support at pressures higher than the unassisted breathing thresholds.

Home: Level of residence or health care facility where the patient was residing prior to hospital admission.

Intention to Treat (ITT): All eligible and consented patients who undergo randomization will be included in the ITT cohort for the purposes of analyzing the primary and secondary study outcomes.

Invasive Mechanical Ventilation: Assisted ventilation delivered by a nasotracheal, orotracheal, or tracheostomy tube.

Legally Authorized Representative: An individual, judicial, or other body authorized under applicable law to consent on behalf of a prospective patient to the patient's participation in the clinical study.

Mortality prior to discharge home before day 90: This primary outcome includes deaths from all causes following randomization in any health care facility prior to discharge home until study day 90. Study subjects still in a health care facility at study day 91 are considered alive for this endpoint.

Funding: National Institutes of Health (National Heart Lung and Blood Institute)

SAEs: Serious Adverse Events Adverse events that are serious and unexpected and have a reasonable possibility that the event was due to a study procedure

Sponsor: The Clinical Coordinating Center at Massachusetts General Hospital

Study day: The day of randomization is study day zero. The next day is study day one etc.

Study hospital: Defined as the hospital where the patient was randomized and enrolled.

Study withdrawal: Defined as permanent withdrawal from study before completion of study activities. If a patient or surrogate requests withdrawal from the study the clinician should seek explicit permission to continue data collection.

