**2. 28-day Ventilator Free Days (VFDs)**

VFDs depend on both duration of ventilation and mortality through study day 28. In participants who survive 28 days, VFD is defined as 28 minus duration of ventilation. Duration of ventilation is counted from the first study day of assisted breathing through the last day of assisted breathing provided the last day is prior to day 28. Otherwise, it is counted from the first study day of assisted breathing through day 28. For participants discharged with assisted ventilation (e.g., to LTAC facility) prior to day 28, a phone call will be required to assess ventilator and vital status at day 28. Participants discharged prior to day 28 on unassisted breathing will be assumed to remain on unassisted breathing through day 28. Isolated periods of ventilation briefer than 24 hours for surgical procedures and ventilation solely for sleep disordered breathing do not count towards duration of ventilation. In participants who never require assisted breathing, duration of ventilation is zero. Participants who do not survive 28 days will be assigned zero VFD. VFD is undefined in participants with chronic/home mechanical ventilation (except solely for sleep disordered breathing) and they will be excluded from this analysis.

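### The ventilator-free-day rule can score a survivor at −1, below death, and leaves patients liberated between a ventilated discharge and day 28 without a determined score; both effects are small

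*Protocol*

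**What the plan says.** Protocol 1.2 fixes the day numbering: "The day of randomization is study day zero. The next day is study day one etc".

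Protocol 3.6.2 item 2 gives the score: "In participants who survive 28 days, VFD is defined as 28 minus duration of ventilation". Duration has two branches. If ventilation ends before day 28, "Duration of ventilation is counted from the first study day of assisted breathing through the last day of assisted breathing". If it does not, "Otherwise, it is counted from the first study day of assisted breathing through day 28". At the two ends of the scale, "In participants who never require assisted breathing, duration of ventilation is zero", and "Participants who do not survive 28 days will be assigned zero VFD" (SAP 2.2 item 2, same rule in the protocol). The SAP repeats the definition unchanged. Neither document states a floor.

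For patients who leave hospital on assisted ventilation before day 28, "a phone call will be required to assess ventilator and vital status at day 28". Protocol 7.3 otherwise collects assisted ventilation over the hospital stay, and Appendix F lists ventilator use at day 28 without mentioning dates.

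Neighbouring endpoints are handled differently. Organ support free days (item 1) are followed to "death, hospital discharge or study day 27, whichever comes first". The renal and vasopressor endpoints (items 3 and 4) explicitly assign zero to patients on support throughout.

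**The concern.** There are two separate points.

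**Day count.** Study days 0 through 28 are 29 days, but the score subtracts from 28. A survivor ventilated over the whole period therefore falls below 0, the value given to deaths. In a composite that sets death at zero, no survivor should score worse than that.

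**Missing input.** The first branch needs the last day of assisted breathing. For a patient discharged ventilated and liberated before day 28, the specified call establishes that the patient is alive and off the ventilator, but not since when. SAP section 5 (Missing Data) allows no imputation except for selected derived variables, with SOFA as the example. Such a patient would be dropped or scored by an unstated rule. VFD is compared by t-test on means, so the choice enters the estimate directly. The SHAMROC ancillary study (Protocol Appendix J) also takes days of mechanical ventilation in the first 28 from the CLOVERS case report form, so the same gap would reach it.

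**Working it through.** The documents give no power calculation or worked score for VFD, so there is no stated figure to reproduce. The check applies the written rule.

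**1. Inclusive count.** Duration = last day − first day + 1, with the last day capped at 28; VFD = 28 − duration.

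| Survivor's ventilation | Duration | VFD |
|---|---|---|
| never | 0 | 28 |
| day 0 only | 1 | 27 |
| days 0–27 | 28 | 0 |
| days 0–28 | 29 | **−1** |
| days 1–28 | 28 | 0 |
| days 5–28 | 24 | 4 |

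Only ventilation on both day 0 and day 28 gives a negative score.

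**2. Does any one 28-day window fit both branches?**
- Days 0–27: the first branch fits. Ventilation on days 5–20 gives 28 − 16 = 12, and the free days are 5 (days 0–4) + 7 (days 21–27) = 12. The second branch does not: days 5–28 score 4, but days 0–4 are five free days.
- Days 1–28: patients first ventilated on day 1 or later fit. Those first ventilated on day 0 score one too low: days 0–20 give 28 − 21 = 7, but days 21–28 are eight free days.

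Neither window reproduces the rule for everyone.

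**3. Elapsed-day count.** Duration = last day − first day. Days 0–28 now score 28 − 28 = 0, so the negative value disappears. But ventilation on day 0 only scores 28 − 0 = 28, the same as never ventilated.

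**4. Size of the day-count error.** It is 1 day per survivor ventilated on both day 0 and day 28. The documents give no share. At an assumed 0.5% to 5% of an arm, the arm mean moves by 0.005 to 0.05 day.

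**5. Undetermined scores.** Take a patient ventilated from day 0, discharged ventilated on day D, alive and off by day 28. The last ventilated day lies between D and 27, so VFD lies between 28 − 28 = 0 and 28 − (D + 1) = 27 − D.

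| D | Possible VFD |
|---|---|
| 7 | 0 to 20 |
| 14 | 0 to 13 |
| 21 | 0 to 6 |

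**6. Size in the comparison.** If one scoring rule is applied to both arms and the affected patients are alike, the errors cancel except for a difference in share. For D = 14, an imbalance of 1 percentage point gives at most 0.01 × 13 = 0.13 day. If instead the arms were handled differently, the bound is 13 days times the share affected.

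Standard error of the difference, 1160 per arm (2320 / 2):
- SD 10 (assumed): 10 × √(2/1160) = 0.42 day
- SD 12 (the respiratory figure in Protocol 9.2 is 12.0): 12 × √(2/1160) = 0.50 day

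So 0.13 day is 0.13/0.50 = 0.26 to 0.13/0.42 = 0.31 of a standard error.

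**The case against.** The intended scale can be inferred. The renal and vasopressor endpoints give zero for support throughout, and hospital free days are counted as elapsed days from randomization. An analyst would probably set the −1 to 0, or count elapsed days and never see it. This stands as a reason to call the matter minor. It does not remove it: the VFD text has no such zero rule, and elapsed counting merges one-day ventilation with none.

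The call form is not in the documents. Ventilator use at day 28 in Appendix F could in practice include dates. Transferred patients are followed to day 28 for hospital free days, and patients not yet home are followed up to day 90 for the primary outcome, so contact is planned anyway. This also stands. The gap is in what is specified and does not show that dates went uncollected.

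Several stronger readings are tempting, but the documents do not support them:
- *That the sickest survivors in general rank below death.* A patient first ventilated on day 1 or later never scores below 0.
- *That every survivor ventilated on day 28 loses one day.* This is true against a 0–27 window, but not for day-1-or-later starters against a 1–28 window.
- *That VFD is a ranked score.* The SAP compares means.
- *That the missing dates could shift the result by a full standard error.* Taking 2% to 4% of an arm at 13 days each gives 0.26 to 0.52 day, but only by moving one arm and leaving the other fixed, on shares the documents do not give.

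**Conclusion.** Both points hold, at minor severity.

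The day-count rule as written gives −1 to a survivor ventilated on both day 0 and day 28, on the inclusive count that is the natural reading of its wording. The effect on an arm mean is 0.05 day or less for assumed shares up to 5%.

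The follow-up specification leaves the score undetermined for patients liberated between a ventilated discharge and day 28. Patients still ventilated at the call are fully determined. The comparison is biased only if the arms differ in the share affected or in how those patients are scored. In the day-14 example that is at most about 0.13 day per percentage point of imbalance in share, roughly a quarter to a third of a standard error for SD 10 to 12. Per patient this is the weightier point.

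VFD is one of 14 secondary endpoints in the protocol. The primary outcome and the sample size are unaffected.

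**What to change.** In Protocol 3.6.2 item 2 and SAP 2.2 item 2, state one 28-day window and apply it to both branches of the duration rule. Study days 0–27 would match item 1 and give scores from 0 to 28; days 1–28 would also work if day 0 is excluded from duration throughout. At minimum, floor VFD at 0. Any of these leaves a survivor ventilated throughout tied with death, not below it.

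Have the day-28 call that is already required for patients discharged ventilated record the last calendar day of assisted breathing, or that the patient is still ventilated. If the form already captures this, say so in both documents.

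The cost is one clause in each document and one extra question per such call.

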5.2 Liberal Fluids Group

Liberal Empiric Fluid Strategy

1. Initiate a 2000 cc crystalloid fluid infusion upon randomization (2000 cc to be complete within 180 minutes of randomization; clinician may extend infusion time at any point during the 2000 cc infusion if indicated for a given patient); monitor for signs of fluid overload
2. Clinical evaluation at the end of first 1000cc:
 - If blood pressure and heart rate have normalized (SBP ≥ 110 mmHg or MAP ≥ 70 mmHg and HR < 90 bpm) and clinical assessment is patient is volume replete, team

- may forego second liter and move to 500cc boluses based on fluid triggers (#5 below); otherwise continue with second 1000cc infusion
3. Maintenance fluids should not be used.
 4. Balanced crystalloid solution (such as lactated Ringers, Hartman's solution, Plasmalyte or Normosol) is recommended, normal saline is permitted.
 5. Subjects receive a 500cc crystalloid fluid bolus for any of the following fluid triggers:
 - a. SBP < 90 mmHg or MAP <65 mmHg
 - b. Lactate > 4 mmol/l and rising in patients with serial lactates measured as part of usual care practices
 - c. Reduced urine output (<30 cc/hour) for > 1 hour (except for ESRD patients)
 - d. Sinus heart rate > 110 beats per minute
 - e. Any measured/clinical assessment of volume status or volume responsiveness (e.g. echo, IVC measurement, CVP, etc) suggesting benefit from additional fluid (as defined by treating clinicians)
 - f. Receiving vasopressors to maintain SBP \geq 90 mmHg or MAP \geq 65 mmHg
 6. Patients should be monitored for volume overload, and fluids may be halted or reduced for clinical evidence of *symptomatic left atrial hypertension based on a clinical diagnosis by the treating or study physician.
 - a. *Clinical features of symptomatic LA hypertension: signs and symptoms of fluid overload (or hydrostatic edema due to left atrial hypertension) include manifestations such as increased respiratory rate, increased use of accessory muscles of respiration, increased bilateral inspiratory crackles, increasing oxygen requirement, or pulmonary edema on chest x-ray likely cardiogenic in origin).
 7. "Rescue vasopressors" recommended (in the form of norepinephrine infusion) for any of the following criteria:
 - a. SBP < 70 mmHg or MAP < 50 mmHg for at least 5 minutes)
 - b. Signs of volume overload (see above) with persistent hypotension/hypoperfusion
 - c. Lactate > 4 mmol/L and rising from previous lactate, after at least 2 hours of therapy

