7.4 Specimen Collection

Plasma will be collected within 2 hours of randomization, at 24 hours, and at 72 hours, frozen, and stored at a biorepository for future research. When consent for genetic testing is specifically obtained, an additional 20 ml of whole blood for future RNA and DNA studies will also be collected. Total blood volume for these draws is approximately 30 ml/day, for a total of approximately 90 ml. Study samples will be sent to a central repository to be stored in accordance with good laboratory practices. Samples will be identified by a coded number during shipment and storage in the central repository.

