For intubated patients, if tolerance criteria for spontaneous breathing trial (1-5 above) are met for at least 30 minutes, the clinical team may decide to extubate. However, the spontaneous breathing trial can continue for up to 120 minutes if tolerance remains in question. If any of criteria 1-5 are not met during unassisted breathing (or 120 minutes has passed without clear tolerance), then the ventilator settings that were in use before the attempt to wean will be restored and the patient will be reassessed for weaning (see section D.2) the following day.

Definition of unassisted breathing

- a) Extubated with face mask, nasal prong oxygen, or room air, OR
- b) T-tube breathing, OR
- c) Tracheostomy mask breathing, OR
- d) CPAP \leq 5 without PS or IMV assistance
- e) Use of CPAP or BIPAP solely for sleep apnea management
- f) Use of a high flow oxygen system

E. Vasopressor Weaning

1. When MAP > 65 mmHg on a stable dose of vasopressor, begin reduction of the vasopressor by greater than or equal to 25% of the stabilizing dose at intervals of less than or equal to 4 hours to maintain MAP greater than or equal to 65 mmHg.
2. Dopamine is considered "discontinued" for vasopressor use and cell assignment when it is weaned to less than or equal to 5 mcg/kg/min, but should continue to be weaned per protocol.

Norepinephrine Equivalents:

- norepinephrine 1 mcg/min
- phenylephrine 2.5 mcg/min
- epinephrine 1 mcg/min
- vasopressin at any dose

F. Time Events Schedule

Measurement/Event	Baseline	(0-6 hrs)	(6-24 hrs)	1	2	3	4	5	6	7	28	90
Demographics, History and Physical	X											
Vital Signs	X				X							
Vasopressor use	X	X	X	X	X	X						
Fluid Administration	X	X	X									
O2, non-invasive and invasive ventilation		X	X									
Daily Fluid Balance (intake and output)				X	X	X	X	X	X	X		
Charlson Score	X											
GCS	X			X	X	X						
Laboratory/microbiology results	A			A	A	A						
Diuretic use				X	X	X	X	X	X	X		
ARDS assessment	X			X	X	X	X	X	X	X		
Plasma Collection	X			X		X						
DNA/RNA	X			X		X						
Plasma for IL-6 and banking	X			X		X						
Disposition											X	
Ventilator, Vasopressor, Renal replacement therapy use											X	
Assessment of infection source											X	
Vital Status											X	X

X=Required
A=When available

G. Adverse Event Reporting and Unanticipated Events

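### The baseline IL-6 sample may be drawn up to 2 hours after randomization, so change in IL-6 can start from a value already affected by treatment and diluted more in the liberal arm

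*Protocol*

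**What the plan says.** Protocol 2.9 and 3.6.2 list change in IL-6 over 72 hours as secondary outcome 13. Its stated purpose is to show how the resuscitation strategy affects inflammation. The sampling rule there is "we will collect blood specimens and measure circulating soluble IL-6 at enrollment, and then at 24, and 72 hours". The schedule in Appendix F has a row "Plasma for IL-6 and banking" with marks under Baseline, day 1 and day 3, and none under its separate 0–6 hour column.

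Protocol 7.4 gives the operational window: "Plasma will be collected within 2 hours of randomization, at 24 hours, and at 72 hours". Nothing in that section or elsewhere says that the first draw must precede study fluid or study vasopressor.

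Protocol 5.2 item 1 for the liberal arm reads "Initiate a 2000 cc crystalloid fluid infusion upon randomization", with "2000 cc to be complete within 180 minutes of randomization; clinician may extend infusion time at any point during the 2000 cc infusion". After the first liter, if blood pressure and heart rate have normalized and the patient is judged volume replete, the team "may forego second liter and move to 500cc boluses based on fluid triggers".

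Protocol 5.1 directs the restrictive arm to vasopressors. It also allows discretionary fluid up to 2 L in total, counting fluid given before randomization, for patients assessed as volume deplete, and it allows rescue fluid at any time the team thinks it best for the patient.

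The SAP does not list IL-6 among its secondary endpoints (1.9, 2.2). Its general method for continuous secondary outcomes (section 5) is a t-test, with no baseline adjustment stated.

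**The concern.** A between-arm comparison of change scores is protected by randomization only if treatment cannot have touched the starting value. Here the labels (enrollment, Baseline) say the first sample is pre-treatment, while the collection window permits one taken after the arms have begun to diverge. The trial is built to make them diverge early: the first separation guideline in Protocol 8.3 is at least 1000 cc over the first 6 hours.

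Two consequences follow from a late draw. First, more crystalloid in the liberal arm lowers the measured starting concentration there, so that arm shows a smaller fall in IL-6 even if the strategies have no effect on inflammation. Second, any real effect of either strategy on IL-6 before the draw is removed from the endpoint by subtraction. The second consequence needs no assumption about dilution.

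**Working it through.** The documents state no sample size, SD or power for IL-6, so there is no plan figure to reproduce. The check has three steps.

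**1. Study fluid given by the time of the draw (document inputs)**

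Liberal arm, 2000 cc at an even rate over 180 minutes:
- by 60 min: 2000 × 60/180 = 667 cc
- by 120 min: 2000 × 120/180 = 1333 cc

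The 1333 cc is not a ceiling. An infusion finished within 120 min gives 2000 cc. One extended to 240 min gives 2000 × 120/240 = 1000 cc, and one extended to 360 min gives 667 cc. If the second liter is skipped and no trigger bolus follows, the volume stops at 1000 cc.

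Restrictive arm, discretionary room without rescue criteria = 2 L minus pre-randomization volume: 1.0 L if 1 L was given before, 0.5 L if 1.5 L, and 0 if 2 L or more.

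**2. Gap in the first IL-6 value (assumed inputs)**

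Assumptions, not in the documents: plasma volume PV = 3 L; share of infused crystalloid in plasma at the draw f = 0.25.

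Gap in log IL-6 = ln[(PV + f × V_lib)/(PV + f × V_res)]

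- 1-h draw, V_lib 0.667 L, V_res 0: ln(3.167/3) = 0.054
- 2-h draw, V_lib 1.333 L, V_res 0: ln(3.333/3) = 0.105
- 2-h draw, V_res 0.5 L: ln(3.333/3.125) = 0.065
- 2-h draw, V_res 1.0 L: ln(3.333/3.25) = 0.025

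Over PV 2.5–3.5 L and f 0.2–0.5, the 2-hour gap runs from about 0.07 to 0.24 with no restrictive fluid, and from about 0.02 to 0.05 with 1 L.

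**3. Effect on a test of 72-hour log change**

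Further assumptions: 1000 samples per arm, SD of log change 1.5 to 2.0, dilution difference gone by 72 hours, every draw at the stated time, no true effect.

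SE = SD × √(2/1000) = 0.067 (SD 1.5) or 0.089 (SD 2.0).

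Two-sided rejection = Φ(−1.96 + gap/SE) + Φ(−1.96 − gap/SE).

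| Draw | Restrictive fluid | Gap | SD 2.0 | SD 1.5 |
|---|---|---|---|---|
| before infusion | 0 | 0 | 5% | 5% |
| 1 h | 0 | 0.054 | 9% | 13% |
| 2 h | 0 | 0.105 | 22% | 35% |
| 2 h | 0.5 L | 0.065 | 11% | 16% |
| 2 h | 1.0 L | 0.025 | 6% | 7% |

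With 500 per arm, the 2-hour draw and no restrictive fluid, SE is 0.095 to 0.126 and rejection is 13–20%. Dilution remaining at 72 hours would partly offset the gap.

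**The case against.** The strongest reply is that the plan intends a pre-treatment sample. The endpoint text says enrollment, Appendix F says Baseline and leaves the 0–6 hour column empty, and the 2-hour limit is only an outer bound that also covers a prompt draw. It could even be read as covering either side of randomization. Section 7.4 describes plasma stored for future research and does not name IL-6; the link is inferred from the identical time points of the two plasma rows in Appendix F. This stands as far as it goes: the sample is not always post-treatment. But nothing makes it pre-treatment, and the labels do not override the only operational window given.

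A reader might infer that dilution affects the liberal arm alone. Protocol 5.1 does not support that: up to 1 L of discretionary fluid, plus rescue fluid, is possible in the restrictive arm. The expected imbalance is one of degree, in the direction the design intends.

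A reader might also take 22–35% as the error rate of the planned analysis. The documents do not support that either. They specify no log scale and no 72-hour IL-6 test, and they give no distribution of draw times or early fluid. The figure requires every draw at the limit, an infusion that is neither slowed nor cut short, and no restrictive fluid.

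Finally, this is one of 14 protocol secondary endpoints. Nothing here touches the primary outcome, sample size or stopping rules.

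**Conclusion.** The point holds in limited form. Followed as written, Protocol 7.4 permits a first IL-6 sample that is post-treatment in both arms and, on expected fluid volumes, more diluted in the liberal arm. A change score from that value can be biased and omits any earlier treatment effect. That much rests on the document text plus the inference that the 7.4 plasma is the IL-6 plasma.

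The size is not fixed by the documents. Under the stated assumptions it ranges from none (draws before the infusion), through near nominal (6–7%, 2-hour draws with 1 L of restrictive fluid), to 22–35% (all draws at 2 hours, no restrictive fluid). The range shows that the problem can matter; it does not estimate what this trial would see. The consequence is confined to one protocol secondary endpoint, which the SAP does not list.

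**What to change.** In Protocol 7.4, state that the first plasma sample is to be drawn before study fluid or study vasopressor starts, without delaying treatment, and record the clock time of the draw. Consent already precedes randomization (Protocol 4.7), so there is room for this. If it is met, study fluid at the first draw is zero in both arms and so is the dilution gap.

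For the analysis, compare log IL-6 at 24 and at 72 hours directly between arms in all randomized patients with samples, rather than as change from a sample that may be post-treatment. Do not select patients, or decide covariate use, by whether the draw preceded treatment. That is a post-randomization event that can differ by arm: liberal fluid starts at randomization, while under Protocol 8.2 starting vasopressors within 60 minutes counts as correct in the restrictive arm.

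Report that a 24-hour level may still carry fluid dilution, since Protocol 8.3 also looks for a 1000 cc difference over 24 hours.

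Reconcile the protocol and SAP: either add IL-6 and its analysis to the SAP or explain its omission.

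The cost is one sentence in 7.4, one data field and a short SAP entry, plus some loss of precision from not using a baseline value.
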